### **Full Analysis Set (FAS)**

The FAS will be defined as all randomized subjects who have at least 1 post-baseline efficacy assessment. The FAS will be the primary population for all the efficacy analyses. The subjects will be analyzed according to the treatment group to which they were randomized.

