4. ANALYSIS POPULATIONS

Population	Definition / Criteria	Analyses Evaluated
Screened	
 Comprise all screened subjects 	
 Study Population
Enrolled	
 All participants who passed screening and entered the study. Included are: only Randomized Participants Note screening failures (who never passed screening even if rescreened) are excluded from the Enrolled population as they did not enter the study. 	
 Study Population
Full Analysis Set 1 (FAS1)	
 Comprise all randomized subjects who have at least 1 post-baseline efficacy assessment. This population will be based on the treatment to which the subject was randomized (this will be applied to FAS2 and FAS3). Any subject who receives a treatment randomization number will be considered to have been randomized. 	
 Study Population Efficacy for the TC 1 (double blind phase)
Full Analysis Set 2 (FAS2)	
 Comprise all randomized subjects who have at least 1 post-2nd treatment efficacy assessment after 2nd treatment. 	
 Efficacy for the TC 2
Full Analysis Set 3 (FAS3)	
 Comprise all randomized subjects who have at least 1 post-3rd treatment efficacy assessment after 3rd treatment. 	
 Efficacy for the TC 3
Safety for double blind phase (SPDB)	
 Comprise all subjects who receive at least one dose of study treatment. This population will be based on the treatment the subject actually received (this will be applied to all safety population). 	
 Safety for the TC 1 (double blind phase)
Safety 1 (SP1)	
 Comprise all subjects who receive at least one dose of GSK1358820 	
 Safety for at least one dose of GSK1358820 treatment
Safety 2 (SP2)	
 Comprise all subjects who receive at least two doses of GSK1358820 	
 Safety for two doses of GSK1358820 treatment
Safety 3 (SP3)	
 Comprise all subjects who receive three doses of GSK1358820. 	
 Safety for three doses of GSK1358820

Population	Definition / Criteria	Analyses Evaluated
		treatment

NOTES :

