6.1.1. Subject Disposition and Populations

For FAS1 population, the number and percentage of subjects who completed the study as well as withdraw early from study will be summarized in each treatment group, along with the reasons for early withdrawal. In addition, the number and percentage of subjects of screening status (enrolled or failed) and the reason for screen failure will be summarized.

Using Screened population, the number and percentage of subjects in each treatment group and non-randomized subjects will be summarized by status (entered, completed or withdrawn) at each epoch (screening phase, double blind phase and open label phase).

The number and percentage of subjects at each centre and country will be summarized (this study includes only Japan as country, but country will be displayed) in each treatment group and total.

Using Screened population, the number of subjects in each population (Screened, passed screening phase (Enrolled), entered each phase (FAS1, FAS2, FAS3, SPDB, SP1, SP2, SP3)) will be summarized total and by treatment group (not including the screened population).

The subjects excluded from any FAS population or SP population will be only listed, not summarized.

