7.2.3. Population of Interest

The secondary efficacy analyses will be based on the FAS1, FAS2 or FAS3 population, unless otherwise specified. Population will depend on TCs.

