7.2.4. Strategy for Intercurrent (Post-Randomization) Events

For binary data, DO=NR rule will be applied to missing data until 12 weeks after 1st treatment. For time to event data, missing data will be treated as censor. All missing data for other secondary endpoints not mentioned above are treated as missing, will not be imputed, unless otherwise specified.

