Secondary Statistical Analyses for Binary data

 This rule will be called as “DO=NR” rule. DO=NR means dropout equals to non-responder.
Secondary Statistical Analyses for Time to Event data
Endpoint(s)

 Time to the subject’s first request for 2nd treatment from the day of 1st treatment Time to the subject’s first qualification for 2nd treatment from the day of 1st treatment
Model Specification

 The above endpoints will be displayed as Kaplan-Meier curves.
Model Results Presentation

 Only summary statistic will be calculated. No statistical model will be applied.
Definition of Event in these endpoints

Time to the subject’s first request for 2nd treatment from the day of 1st treatment
 
 Event is considered to occur at “Date of subject status” in eCRF when the following items meet for the first time. 
 Answer to question “Did patient initiate request for retreatment?” in eCRF = “Yes” Regardless of answer to question “Did patient qualify for retreatment?” in eCRF 
Time to the subject’s first qualification for 2nd treatment from the day of 1st treatment
 
 Event is considered to occur at “Date of subject status” in eCRF when the following items meet for the first time. 
 Answer to question “Did patient initiate request for retreatment?” in eCRF = “Yes” Answer to question “Did patient qualify for retreatment?” in eCRF = “Yes” 
(Time to the subject’s first request for 2nd treatment from the day of 1st treatment) = (the earliest date when “Yes” response to the eCRF question “Did patient initiate request for retreatment?”) – the day of first treatment + 1
 
(Time to the subject’s first qualification for 2nd treatment from the day of 1st treatment) = (the earliest date when “Yes” response to the eCRF question “Did patient qualify for retreatment?”) – the day of first treatment + 1

Censoring

 If the subject withdraws the study prematurely before receiving 2nd treatment, this subject will be regarded as censored at the date of study withdraw. If the subject completes the study without request for the 2nd treatment, the subject will be regarded as censored at the date of study complete.

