11.10.10. ICH Listings

ICH : Listings						
No.	Population	IDSL / TST ID / Example Shell	Title	Programming Notes	Report at Interim	Report at Final
Subject Disposition						
1.	Screened	ES7	Listing of Reasons for Screen Failure	Journal Guidelines	Y	
2.	FAS1	ES2	Listing of Reasons for Study Withdrawal	ICH E3	Y	Y
3.	FAS1	BL1	Listing of Subjects for Whom the Treatment Blind was Broken	ICH E3	Y	Y
4.	FAS1	TA1	Listing of Planned and Actual Treatments	IDSL	Y	
Protocol Deviations						
5.	FAS1	DV2	Listing of Important Protocol Deviations	ICH E3	Y	Y
6.	FAS1	IE3	Listing of Subjects with Inclusion/Exclusion Criteria Deviations	ICH E3	Y	Y
Populations Analysed						
7.	Enrolled	SP3	Listing of Subjects Excluded from Any Population	ICH E3	Y	Y
Demographic and Baseline Characteristics						
8.	FAS1	DM2	Listing of Demographic Characteristics	ICH E3	Y	
9.	FAS1	DM2	Listing of Baseline Disease Characteristics		Y	
10.	FAS1	DM9	Listing of Race	ICH E3	Y	
Current and Past Medical Conditions, Prior and Concomitant Medications						
11.	FAS1	MH2	Listing of Medical Conditions		Y	Y
12.	FAS1	CM3	Listing of Concomitant Medications	IDSL	Y	Y

CONFIDENTIAL

204948

ICH : Listings						
No.	Population	IDSL / TST ID / Example Shell	Title	Programming Notes	Report at Interim	Report at Final
13.	FAS1	CM3	Listing of Prior or Concomitant NDO Medications	IDSL	Y	
Exposure and Treatment Compliance						
14.	FAS1	EX3	Listing of Exposure Data	ICH E3	Y	Y
Adverse Events						
15.	SPDB	AE8	Listing of All Adverse Events	ICH E3	Y	Y
16.	SPDB	AE7	Listing of Subject Numbers for Individual Adverse Events	ICH E3	Y	Y
17.	SPDB	AE2	Listing of Relationship Between Adverse Event System Organ Classes, Preferred Terms, and Verbatim Text	IDSL	Y	Y
Serious and Other Significant Adverse Events						
18.	SPDB	AE8	Listing of Fatal Serious Adverse Events	ICH E3	Y	Y
19.	SPDB	AE8	Listing of Non-Fatal Serious Adverse Events	ICH E3	Y	Y
20.	SPDB	AE14	Listing of Reasons for Considering as a Serious Adverse Event	ICH E3	Y	Y
21.	SPDB	AE8	Listing of Adverse Events Leading to Withdrawal from Study / Permanent Discontinuation of Study Treatment	ICH E3	Y	Y
22.	SPDB	AE8	Listing of Special Interest Adverse Events	ICH E3	Y	Y
Hepatobiliary (Liver)						
23.	SPDB	MH2	Listing of Medical Conditions for Subjects with Liver Stopping Events	IDSL	Y	Y
24.	SPDB	SU2	Listing of Substance Use for Subjects with Liver Stopping Events	IDSL	Y	Y
25.	SPDB	LIVER5	Listing of Liver Monitoring/Stopping Event Reporting	IDSL	Y	Y

CONFIDENTIAL

204948

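### FAS1 omits any randomised subject with no post-baseline efficacy assessment, so DO=NR never reaches that subject, whose deviations and non-AE withdrawal reason have no planned display

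*SAP*

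**What the plan says.** **Population.** SAP section 4 restricts FAS1 by post-randomisation data: "Comprise all randomized subjects who have at least 1 post-baseline efficacy assessment". It takes a broad view of who is randomised: "Any subject who receives a treatment randomization number will be considered to have been randomized". The restriction comes from the protocol: "The FAS will be defined as all randomized subjects who have at least 1 post-baseline efficacy assessment" (Protocol 9.3.1).

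**Binary endpoints.** SAP 7.2.3 sets the population: "The secondary efficacy analyses will be based on the FAS1, FAS2 or FAS3 population, unless otherwise specified". For TC1 this is FAS1, and the display list puts Table 2.54 (100%, ≥75% and ≥50% reduction in incontinence) and Table 2.57 (TBS) on it. On missing data, SAP 7.2.4 says: "For binary data, DO=NR rule will be applied to missing data until 12 weeks after 1st treatment". SAP 7.2.5.1 explains the label: "DO=NR means dropout equals to non-responder". SAP 11.6.3 also counts a missing TBS answer as not positive.

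**Disposition and deviations.** SAP 6.1.1 begins "For FAS1 population, the number and percentage of subjects who completed the study" and goes on to early withdrawal and its reasons. In SAP 11.10 these become Table 1.1 and Listing 2 ("Listing of Reasons for Study Withdrawal"), both on FAS1. Blind breaks (Listing 3), planned against actual treatment (Listing 4), and deviations (Table 1.5, Listings 5 and 6) are on FAS1 too.

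**The concern.** A rule that counts dropouts as non-responders is meant to stop a responder rate from improving because people leave. It can do that only for subjects in the denominator. FAS1 sets the denominator by whether efficacy was ever assessed after baseline, so the subject with the least follow-up is removed instead of being counted as a non-responder.

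The same filter governs the displays from which a reader judges attrition and conduct. If a subject is withdrawn after a code break, is lost to follow-up or refuses further visits before any efficacy assessment, the reason for leaving, the code break and any deviation fall outside the tables and listings meant to show them. With 15 per arm, each subject is 1/15 = 6.7 percentage points of an arm, so even one is noticeable.

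**Working it through.** **1. The plan's own figures.** None bears on this point: neither document gives a dropout rate or an expected responder rate. The only planning input used below is 15 subjects per arm (Protocol 9.2.1).

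**2. Who is lost.** Leaving early is not enough.
- Diary, KHQ and TBS are all scheduled at the withdrawal visit (Protocol Table 1).
- Withdrawal visits are slotted by the assessment windows (SAP 11.7.1), and the TC1 Week 2 efficacy window runs from Day 2 to Day 29 (SAP 11.3.1).
- One valid diary day is enough for a visit (SAP 11.6.3).

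So a subject who leaves on Day 5 but completes any of these is in FAS1, and DO=NR applies. The subject who is lost is one with no post-baseline efficacy assessment at all, for example someone lost to follow-up, someone who declines the withdrawal visit, or someone randomised but never injected.

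**3. Where that subject appears** (SAP 6.1.1 and 11.10).

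| Information | Display | Population | Included? |
|---|---|---|---|
| Responder, TBS (TC1) | Tables 2.54, 2.57 | FAS1 | No |
| Completion, withdrawal reason | Table 1.1, Listing 2 | FAS1 | No |
| Blind break, planned/actual treatment | Listings 3, 4 | FAS1 | No |
| Deviations | Table 1.5, Listings 5, 6 | FAS1 | No |
| Status by epoch | Table 1.2 | Screened | Yes, but SAP 6.1.1 mentions no reasons |
| Count in each population | Table 1.6 | Screened | Yes, as a count by arm |
| Exclusion from a population | Listing 7 | Enrolled | Yes |
| AEs leading to withdrawal | Listing 21 | SPDB | Only if dosed and AE-related |

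**4. Effect on a responder rate.** Assumptions: 15 randomised per arm, *a* active responders with *a* from 6 to 10, and one active subject with no efficacy assessment. The gap is a/14 − a/15 = a/210.

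| a | FAS1, a/14 | All randomised, a/15 | Gap (points) |
|---|---|---|---|
| 6 | 42.9% | 40.0% | 2.9 |
| 8 | 57.1% | 53.3% | 3.8 |
| 10 | 71.4% | 66.7% | 4.8 |

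With two such subjects the gap is a/13 − a/15 = 2a/195, which is 6.2 points at a = 6 and 10.3 at a = 10. With none it is zero.

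**5. Effect on the odds ratio.** The case is 8 active and 3 placebo responders, with Woolf 95% intervals (the SAP does not name an interval method).
- All randomised, 8/15 against 3/15: (8 × 12)/(7 × 3) = 4.57 (0.90 to 23.14).
- FAS1, one active subject lost, 8/14 against 3/15: (8 × 12)/(6 × 3) = 5.33 (1.02 to 27.76).
- FAS1, one placebo subject lost instead, 8/15 against 3/14: (8 × 11)/(7 × 3) = 4.19.

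The direction therefore depends on the arm.

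**6. Primary analysis.** The MMRM does not impute (SAP 7.1.4 and 11.7.3). A subject with no post-baseline value supplies no record to it, so the estimate is the same on FAS1 or on all randomised subjects.

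**The case against.** The strongest reply is that FAS1 follows the protocol word for word in substance, that requiring one post-baseline assessment is a pre-specified choice, and that DO=NR is a rule for missing data inside the analysis set. On that view there is no contradiction, only a reviewer's preference for a wider set. It stands that the SAP does not depart from the protocol. It does not remove the gap: the SAP explains its rule as dropout equals non-responder, and the population keeps that rule from the clearest dropout.

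A reader might infer that anyone who leaves before Week 2 is removed. The documents do not support that, because withdrawal-visit diary, KHQ or TBS data can bring such a subject into FAS1.

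A reader might also infer that these subjects disappear from all reporting. They do not. Tables 1.2 and 1.6 count them, Listing 7 lists them, and Listing 21 shows AE-related withdrawal in dosed subjects. SAP 11.7.2 also asks the study report to document exclusions with their reason, and SAP 11.7.1 promises listings of withdrawn subjects' available data unless otherwise specified. These are general statements. The display list assigns withdrawal reasons and deviations to FAS1, and a reason for exclusion from an analysis is not a reason for leaving the study.

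Finally, the number affected may be zero. Treatment is a single injection and treatment discontinuation is not defined (SAP 7.1.4), so loss before any assessment generally means leaving the study itself. That is fair, and it limits the weight of the point.

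**Conclusion.** The point holds in a narrow form and is minor. It concerns only randomised subjects with no post-baseline efficacy assessment at all. For them, DO=NR has no effect in Tables 2.54 and 2.57, and deviations and non-AE withdrawal reasons have no planned display.

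Its size rests on assumption, since the documents give neither dropout nor responder rates. One such active subject, with 15 per arm and 6 to 10 responders, raises the active rate by 2.9 to 4.8 points. One such placebo subject, with 3 to 5 placebo responders, raises the placebo rate by 3/210 = 1.4 to 5/210 = 2.4 points and so works against the drug. With no such subject the rates do not change.

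It would be wrong to conclude that the plan systematically favours GSK1358820, or that the primary result is biased. Nor should weight be put on a lower limit moving from 0.90 to 1.02 in one assumed case: both documents state that no formal hypothesis is evaluated (Protocol 9.1, SAP 2.4). What is affected is the secondary binary estimates and the transparency of attrition and deviations.

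**What to change.** **Disposition and deviations.** Run Tables 1.1 and 1.5 and Listings 2 to 6 on the Enrolled population, which SAP section 4 already defines as randomised participants only. This is a change of population label and needs no new data.

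**Responder and TBS tables.** For Tables 2.54 and 2.57, apply DO=NR to Week 12 to all randomised subjects (Enrolled), analysed as randomised. This is more than a relabel, because the protocol makes the FAS the primary population for all efficacy analyses. Either record the change in SAP Table 1 (section 2.1), or keep the FAS1 tables and add the all-randomised version as a supplement. SPDB is not a substitute, since it groups subjects by treatment actually received. No existing population is randomised and treated but grouped as randomised. With Enrolled, a subject randomised but never injected counts as a non-responder, and the SAP should say so.

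**Cost.** A slightly less favourable rate in any affected arm, and one recorded departure from, or supplement to, the protocol FAS. If no subject is affected, the FAS1 and all-randomised results coincide.

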4.1. Protocol Deviations

Important protocol deviations (including deviations related to study inclusion/exclusion criteria, conduct of the trial, patient management or patient assessment) will be summarised and listed.

Protocol deviations will be tracked by the study team throughout the conduct of the study in accordance with the Protocol Deviation Management Plan [25JUL2018, version 1.4].

- Data will be reviewed prior to unblinding and freezing the database to ensure all important deviations and deviations which may lead to exclusion from the analysis are captured and categorised on the protocol deviations dataset.
- This dataset will be the basis for the summaries and listings of protocol deviations.

A separate listing of all inclusion/exclusion criteria deviations will also be provided. This summary will be based on data as recorded on the inclusion/exclusion page of the eCRF.

5. CONSIDERATIONS FOR DATA ANALYSES AND DATA HANDLING CONVENTIONS

5.1. Study Treatment & Sub-group Display Descriptors

Treatment Group Descriptions for TC1			
RandAll NG		Data Displays for Reporting	
Code	Description	Description	Order in TLF
A	GSK1358820 200U	GSK1358820 200U	2
B	Placebo	Placebo	1

In TC1, the treatment group description will be used as above table.

Treatment comparisons will be displayed as follows using the descriptors as specified:

1. GSK1358820 200U vs Placebo

In re-treatment, all subjects who met re-treatment criteria will be administered GSK1358820 200U, therefore, but the treatment group description as below table will be used except for TC1.

Treatment Group Descriptions except for TC1			
RandAll NG		Data Displays for Reporting	
Code	Description	Description	Order in TLF
A	GSK1358820 200U	GSK1358820 200U / GSK1358820 200U	2
B	Placebo	Placebo / GSK1358820 200U	1

5.2. Baseline Definitions

For all endpoints (except as noted in baseline definitions) the baseline value will be the latest pre-dose assessment with a non-missing value, including those from unscheduled visits. For urinary diary data, the baseline value will be the latest pre-dose 3-day diary which has at least one valid diary day. If time is not collected, Day 1 assessments are assumed to be taken prior to first dose and used as baseline. This baseline means “study baseline”. “Study baseline” will be used for all analyses using baseline data (e.g., change from baseline).

Unless otherwise stated, if baseline data is missing no derivation will be performed and baseline will be set to missing.

5.3. Multicentre Studies

In this multicentre local study, randomization will be presented by investigative site.

In primary efficacy analysis, centres will not be included in statistical model. Treatment-by-centre interaction will not be evaluated.

5.4. Examination of Covariates, Other Strata and Subgroups

5.4.1. Covariates and Other Strata

The list of covariates and other strata may be used in descriptive summaries and statistical analyses, some of which may also be used for subgroup analyses. Additional covariates and other strata of clinical interest may also be considered.

Category	Item	Details
Strata	NDO etiology (SCI with neurological injury level C5 to C8, SCI with neurological injury level T1 or below, or MS)	This is the randomization strata factor. This factor will NOT be included in all statistical model, because the numbers of subjects of SCI with neurological injury level C5 to C8 and MS are small. Descriptive summaries results will also not be provided by each category.
Covariate	Nothing	Considering small number of subjects in this study, subgroup analysis will not be meaningful.

•

